Study Population:	Individuals 14 years and older, assigned female sex at birth, who are seeking care at a UPMC Magee-Womens Hospital (MWH) participating PAT study office complaining of symptoms of vaginitis
Study Duration:	Approximately two weeks of follow-up per participant with a projected accrual period of approximately 12 months
Study Sites:	Obstetric/gynecologic (OB/GYN) practices/offices located within UPMC Magee-Womens Hospital (MWH) and outpatient centers affiliated with the Department of OB/GYN or MWH
Study Design:	Two arm, randomized, single center trial of usual care vs. Xpert® Xpress MVP (multiplex vaginal panel; Cepheid, Sunnyvale, CA) directed care for vaginitis diagnosis and treatment

Individuals who are complaining of vaginitis symptoms and are seeking care at one of the PAT study participating offices/departments within or affiliated with MWH will be invited to participate. In this study, the office visit will serve as the enrollment (index) visit. Following informed consent, participants will complete a brief questionnaire and self-collect three vaginal swabs for three tests that are FDA-cleared for vaginitis diagnosis: Xpert® Xpress MVP, BD MAX™ Vaginal Panel (Becton-Dickinson, Franklin Lakes, NJ), and BD Affirm™ VPIII Microbial Identification Test (Affirm™ VPIII; Becton-Dickinson). Participants will be randomized (1:1) into one of two arms after collecting swabs.

In Arm 1, vaginitis diagnosis and treatment will be based on usual provider evaluation and treatment during the office visit. The Xpert® Xpress MVP test will be batched with delayed results made available to the provider following the participant's 2-week study follow-up telephone contact.

In Arm 2, the Xpert® Xpress MVP test will be run in real time as a point of care (POC) test at the time of the office visit and the results will be made available to the provider in approximately one hour. Providers will be asked to use the MVP test result for diagnosis and treatment of the participant.

All participants, regardless of arm, will complete a follow-up telephone contact approximately two weeks after their office/medical visit to assess symptom resolution and satisfaction.

The study will include review and collection of electronic medical record information related to the office/medical visit (i.e., evaluation, testing, diagnosis and treatment).

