In a published study of 290 women seeking health care for symptoms of vaginitis, more than half had a lab-diagnosed condition, with 30% of women having BV, 34% having VVC and 7% having TV based on laboratory testing¹⁸. This study documented that only one in five women having symptoms of vaginitis had CDC-recommended point-of-care testing, such as assessment of vaginal pH, microscopic examination of vaginal fluid, or the whiff test, is performed when women

present with vaginal symptoms in primary women's health care settings. Overall, four of 10 women seeking health care for symptoms of vaginitis in this study were prescribed inappropriate treatments. Return visits for symptoms of vaginitis were common, occurring over the next 3 months in 20% of the women. The frequency of return visits ranged from 17% of women with VVC, 35% of women having BV, and 42% of women with TV. Surprisingly, follow-up visits for vaginal symptoms were also common for women having no lab-diagnosed vaginitis at the index visit, with 12% of women returning with symptoms of vaginitis. The women who were prescribed unneeded treatment were significantly more likely to return with symptoms of vaginitis in the subsequent three months versus those who were not treated (22% versus 6%, $p=0.02$). Empiric treatment of women having symptoms of vaginitis is common and is perceived to cause no harm. However, these data suggest that empiric treatment of women having symptoms, but no infectious cause of vaginitis, may result in more symptom-triggered visits and a greater health care burden. Similarly, low rates of clinical evaluation of vaginitis have been reported among women referred for management of recurrent vaginitis¹⁹.

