1. To compare the proportion of study participants who are prescribed appropriate treatment at index visit or within 24 hours of index visit based on the provider assessment conducted at the time of the office/medical visit (Arm 1) to the proportion of study participants who are prescribed appropriate treatment when Xpert® Xpress MVP testing is performed and reported on the day of the office visit (Arm 2).
 - a. Appropriate treatment is defined as CDC recommended or FDA approved treatment based on diagnosis from the self-collected samples. A positive result from both FDA cleared molecular tests (Xpert® Xpress MVP; BD MAX™ Vaginal Panel) will be considered the gold standard for the diagnosis of vaginitis/vaginosis for data analysis.

2.2 Secondary Objectives:

1. To compare the accuracy of provider's diagnosis of vaginitis (usual care) to the diagnosis of vaginitis based on the results of the Xpert® Xpress MVP test at the office/medical visit.
2. To compare the proportion of women who experience resolution of vaginitis symptoms at the two week follow up contact after undergoing evaluation with a novel POC molecular test to the proportion of women with resolution of vaginitis symptoms after evaluation by their provider's usual care.
3. To evaluate participant satisfaction with usual care vs point of care testing for vaginitis. Questionnaires will be administered to all participants at the office visit and approximately two weeks after enrollment.
4. To compare the accuracy of a nonamplified probe-based platform (BD Affirm™ VPIII) that tests for *Candida*, *Trichomonas vaginalis* and *Gardnerella vaginalis* compared to the results of two FDA-cleared molecular tests for diagnosis of vaginitis/vaginosis: two NAAT platforms (Xpert® Xpress MVP; BD MAX™ Vaginal Panel).

2.3 Exploratory Objectives:

1. Assess the impact of vaginitis symptoms on patient quality of life and productivity through use of the Sheehan Disability Scale (SDS), which will be administered at enrollment. Results will be assessed overall and stratified by participant-reported severity based on the Patient Global Impression of Severity (PGIS) instrument.
2. To assess provider satisfaction/treatment confidence with usual care assessment vs Xpert® Xpress MVP testing through the Healthcare Provider Sub Study.

3. Study Population

The inclusion and exclusion criteria in this section will be utilized to ensure the appropriate selection of study participants.

3.1 Recruitment:

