In both arms, the two additional swabs will be tested in the MWRI Lab for *Trichomonas vaginalis*, *Candida* species and *Gardnerella vaginalis* using the BD Affirm™ VPIII and for *Candida*, *Trichomonas vaginalis* and bacterial vaginosis using the BD MAX™ Vaginal Panel. The results from the BD Affirm™ VPIII and BD MAX™ Vaginal Panel will be used for research purposes only and will not be shared with the provider or participant, regardless of the arm of the study. The BD MAX™ result will be used to evaluate the Primary Objective, as appropriate treatment is defined as CDC recommended or FDA approved treatment based on diagnosis from concordant NAAT (Xpert® Xpress MVP and BD MAX™ Vaginal Panel) results from the self-collected enrollment swabs. The results from the Xpert® Xpress MVP and BD MAX™ Vaginal Panel will be compared to the Affirm VPIII results as a secondary objective to assess the accuracy of this testing system.

Participants will be contacted approximately two weeks (14-day target with window of 10-21 days) following the visit to complete a follow-up questionnaire including questions such as current (or resolution of) symptoms, compliance with treatment, additional care or treatment, and satisfaction/comfort with self-collection of swabs, satisfaction with diagnosis and treatment, and a validated symptom score (PGIC). The questionnaires will take less than ten minutes to complete; answers will be entered into the PAT Study REDCap database by research staff.

For participants in Arm 1, following the 2-week follow-up contact, the researcher will share the Xpert® Xpress MVP results with the office staff, and enter the results into the electronic medical

record as determined by the MWH Point of Care (POC) Committee. It will be the responsibility of the provider to provide additional treatment if needed.

Up to four weeks following enrollment, a researcher will perform an EMR chart review to include but not limited to the following:

- Collection of data from the office/medical (enrollment/index) visit, including provider information, assessment and treatment prescribed
- Review/collection of tests performed/ordered at the office/medical visit and associated results, to include STI testing
- Subsequent contact, testing and/or vaginitis treatment following enrollment and/or based on delayed Xpert® Xpress MVP results.
- Treatment switches

4.3 HEALTHCARE PROVIDER SUB STUDY:

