7.3 Secondary and Exploratory Endpoint Analyses

Patient and Provider satisfaction with usual care versus point of care testing will be evaluated on a 5-point Likert scale with 1 being very satisfied to 5 being very dissatisfied. Responses will be dichotomized for analyses (very satisfied and satisfied versus all others). Differences in patient and provider satisfaction with and the proportion of women who experience resolution of vaginitis symptoms after treatment based on usual care and point of care testing will be evaluated using Fisher's exact test.

A positive result from both of the two FDA cleared molecular tests (Xpert® Xpress MVP; BD MAX™ Vaginal Panel) will be considered the gold standard for the diagnosis of vaginitis/vaginosis for analysis. Samples yielding discordant results will be retested using the reserve sample. Samples which are discordant after retesting will be evaluated separately.

Fisher's exact test will be used to compare the provider's diagnosis of vaginitis based on usual care to the diagnosis based on the results of point of care testing. The sensitivity, specificity, negative and positive predictive values of the BD Affirm™ VPIII test for *Candida*, *Trichomonas vaginalis* and *Gardnerella vaginalis* will be calculated and compared to those of the two FDA-cleared tests using the test for equality of proportions.

Patient quality of life and productivity will be assessed using the Sheehan Disability Scale (SDS) where 0 indicates no functional impairment and 30 high functional impairment. Descriptive statistics will be used to assess overall SDS scores. Differences in SDS scores by participant-reported severity will be evaluated using Kruskal-Wallis (continuous SDS score) and Fisher's exact (categorized SDS score) tests.

[figure not shown]
8. Costs and Payments:

The cost for the testing for vaginitis using the self-collected molecular methods will be covered by the study in both arms of the study. The cost of routine clinical care visits, which may include other diagnostic testing will not be covered by the study. Treatment may be prescribed by the healthcare provider according to usual care; the cost of this treatment will not be covered by the study.

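### Section 7.3 describes symptom resolution after treatment, secondary objective 2 compares women after evaluation, and no analysis population settles the denominator

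*Combined protocol and SAP*

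**What the plan says.** Secondary objective 2 (section 2.2) sets "resolution of vaginitis symptoms at the two week follow up contact after undergoing evaluation with a novel POC molecular test" against "the proportion of women with resolution of vaginitis symptoms after evaluation by their provider's usual care". Both sides are defined by evaluation, and neither is conditioned on treatment.

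Section 7.3 names the quantity for Fisher's exact test as "the proportion of women who experience resolution of vaginitis symptoms after treatment based on usual care and point of care testing". It does not say whether women who received no treatment are counted.

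Other parts of the protocol bear on the denominator:

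- The study summary plans the outcome for everyone: "All participants, regardless of arm, will complete a follow-up telephone contact approximately two weeks after their office/medical visit to assess symptom resolution and satisfaction". Section 4.2 gives the timing as a "14-day target with window of 10-21 days".
- Treatment is not universal. Section 8 states: "Treatment may be prescribed by the healthcare provider according to usual care". Under section 4.2, Arm 2 providers are asked, but not required, to diagnose and treat on the MVP result.
- Sections 7.1 to 7.3 define no analysis population for this or any other endpoint.

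**The concern.** Evaluation and treatment are different events in this trial. Every participant is evaluated, but only some are treated, and the decision to treat comes after randomisation. It is also the decision that the test is meant to alter. The Background takes the view that "these data suggest that empiric treatment of women having symptoms, but no infectious cause of vaginitis, may result in more symptom-triggered visits", so leaving uninfected women untreated is part of how test-directed care is expected to help.

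An analyst who followed section 7.3 literally could restrict the comparison to treated women. The two treated groups would then be selected by different rules and could hold different proportions of infected and uninfected women. A difference in resolution could reflect that mix alone. The untreated uninfected women, among whom the Background expects a benefit, would not be counted. With the denominator open, the choice could also be made after the data are seen.

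**Working it through.** **The plan's own figure.** The documents give no number for symptom resolution. The only power statement is for the primary endpoint in section 7.1: 150 per arm, 75% against 90%, two-sided 0.05, 91%. Exact enumeration of Fisher's test gives 91.6%, so that figure reproduces. It is not in dispute; the same routine gives the rejection rates below.

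**Inputs from the documents.** There are 150 women per arm (section 7.1). More than half had a lab-diagnosed condition in the cited earlier study (section 3.1), taken here as 55% to 65%. That study also reports return with symptoms in 12% of women with no lab-diagnosed vaginitis, and in 22% after unneeded treatment against 6% without treatment (Background). If all three figures refer to women without a lab diagnosis, the treated share t among them solves 22t + 6(1 − t) = 12. Hence 16t = 6 and t = 37.5%, or about 31% to 44% allowing for rounding.

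**Assumed inputs.** Treatment shares by infection status, and resolution rates, are not in the documents. The 40% used below for uninfected women in Arm 1 is close to the 37.5% just derived; the other values are illustrative.

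**Worked case, treatment having no effect on symptoms.** Take 60% infected. Arm 1 treats 75% of infected and 40% of uninfected women; Arm 2 treats 95% and 10%. Resolution is 80% if infected and 50% if not, in both arms.

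- Arm 1 treated: 0.60 × 0.75 = 0.45 infected and 0.40 × 0.40 = 0.16 uninfected, total 0.61. Resolution = (0.45 × 0.80 + 0.16 × 0.50)/0.61 = 0.44/0.61 = 72.1%.
- Arm 2 treated: 0.60 × 0.95 = 0.57 and 0.40 × 0.10 = 0.04, total 0.61. Resolution = (0.57 × 0.80 + 0.04 × 0.50)/0.61 = 0.476/0.61 = 78.0%.
- Treated-only difference: 5.9 points. The treated groups are 0.16/0.61 = 26.2% and 0.04/0.61 = 6.6% uninfected.
- All randomised: 0.60 × 0.80 + 0.40 × 0.50 = 68% in both arms, difference 0.

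**Range.** Infected share 55% to 65%, no treatment effect, number treated fixed at its expected value:

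| Treated, infected/uninfected (%), Arm 1 vs Arm 2 | Resolution, infected/uninfected (%) | Treated-only difference, Arm 2 − Arm 1 (points) | Fisher rejects, treated-only |
|---|---|---|---|
| 75/40 vs 95/10 | 80/50 | +5.1 to +6.7 | 11.0–15.1% |
| 75/25 vs 90/10 | 80/50 | +2.9 to +3.9 | 6.1–7.6% |
| 75/40 vs 95/10 | 70/50 | +3.4 to +4.5 | 6.5–7.9% |
| 75/25 vs 90/10 | 70/50 | +1.9 to +2.6 | 4.8–5.4% |
| 75/40 vs 95/10 | 50/80 | −6.7 to −5.1 | 9.2–13.1% |
| 75/25 vs 90/10 | 50/80 | −3.9 to −2.9 | 5.2–6.8% |

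With all 150 per arm as the denominator, the true difference is 0 and Fisher rejects 3.7–3.9% of the time throughout.

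**If treatment does work.** Let resolution be 80% in treated infected, 30% in untreated infected and 50% in uninfected women. With 55% infected and the larger shift in treatment shares, the all-randomised difference is 5.5 points and the treated-only difference 6.7. With 65% infected and the smaller shift, they are 4.9 and 2.9. The treated-only figure can therefore overstate or understate the effect that the objective asks about.

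**The case against.** The strongest reply is that section 7.3 never excludes anyone. It speaks of the proportion of women, as section 7.2 does for the whole-arm primary comparison. Its phrase about treatment may simply name the two care strategies, since the study summary describes Arm 1 in terms of diagnosis and treatment under usual care, and section 4.2 describes Arm 2 in terms of the MVP result. The sentence is loosely built. The objective and the follow-up schedule both point to all participants. This reply largely stands. A reader might infer that the plan restricts the analysis to treated women, but the documents do not say so. What remains is a mismatch in wording that no analysis population resolves.

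A second reply is that the size and sign of any bias are assumed. This also stands. A reader might infer that a treated-only analysis would favour Arm 2, but the documents do not support a direction. Their only related figures are three-month returns with symptoms: 12% in women without a lab diagnosis, against 17% (VVC), 35% (BV) and 42% (TV). If two-week resolution followed that pattern, the bias would run against Arm 2, although late returns are only a proxy.

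Third, omitting baseline severity is not an error. An unadjusted Fisher test of randomised arms is valid; adjustment offers precision only. Finally, this is one of four secondary objectives, it carries no sample-size claim, and the primary endpoint is unaffected.

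**Conclusion.** The point holds as a conflict of wording with an undefined denominator. Objective 2 concerns women evaluated, section 7.3 speaks of resolution after treatment, and nothing states which women are counted. If section 7.3 were applied literally, the comparison would condition on a post-randomisation decision that the intervention is designed to change. It could then show a spurious difference of about 3 to 7 points in either direction with a 30-point gap in resolution between infected and uninfected women, or about 2 to 4.5 points with a 20-point gap. These sizes rest on assumed treatment shares and resolution rates.

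It would go too far to conclude that the planned analysis has lost the protection of randomisation. That follows only if the treated-only reading is adopted, and the documents do not commit to it. The change is still worth making, because it removes the ambiguity before the data are seen.

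**What to change.** In section 7.3, replace the phrase about treatment based on the two kinds of care with resolution at the two-week contact among all randomised women, by assigned arm, whether or not treated. Report the risk difference with a 95% CI adjusted for baseline PGIS. Label any treated-only comparison as supportive.

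Two details belong with the new sentence. An all-randomised denominator needs a stated rule for women not reached at the call, and the documents give none. Also, section 4 leaves the order of questionnaire and swabs open, while randomisation and disclosure of the arm follow the swabs. PGIS should therefore be recorded before the arm is known if it is to serve as a baseline covariate.

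The cost is a few sentences and no new data, since all participants are to be called and PGIS is already in the schedule of evaluations. The downside is that untreated women dilute a pure effect of treatment, but that effect is not the stated objective.

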A researcher who is familiar with/has access to the EMR will abstract information from the participant's chart from the office (enrollment/index) visit and up to approximately one month following the enrollment visit. The data abstracted will be information from the office visit for vaginitis including but not limited to demographics, chief complaint, length of symptoms, assessment of discharge, associated testing, impression and treatment. Any subsequent visits or encounters over approximately one month will be reviewed by a researcher to capture test results, prescribed treatment, treatment switches, etc. Information may also be reviewed/collected on subsequent contacts and treatment.

The abstracted data may be documented on a paper case report form and then entered into the PAT study REDCap database or may be directly entered into the database. The REDCap system is housed at the University of Pittsburgh; the database will be built and maintained by the data management team in Pittsburgh and will be used to enter and manage study data. REDCap is a secure, web-based application designed for clinical trial data collection. REDCap employs various methods to protect the data stored in the software application's backend database against data breaches.

5. Specimen Processing and Testing

The sites will adhere to the standards of good clinical laboratory practice and standard operating procedures for proper collection, processing, labeling, handling, transport, and storage of specimens.

- Laboratory Test Procedures
 - Cepheid Xpert® Xpress MVP: Immediately upon collection, the vaginal swab will be transferred to the Xpert® Swab Specimen Collection Kit and stored at ambient temperature (15-28°C). Specimen collection, storage and transport will be according to the manufacturer's instructions.
 - Arm 1: The sample will be tested within 17 days of collection. The clinical research staff will provide the result to the provider after completion of the participant's two week follow-up telephone contact.
 - Arm 2: The sample will be run by a clinical researcher as a point of care test in/near one of the PAT study participating offices. The result will immediately be given to the provider/entered into the EMR. Providers who agree to participate in this study will be asked to use the result of the FDA cleared test for diagnosis and treatment, but they will not be required to do so.

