7.1 Sample size calculations

The primary endpoint is the proportion of study participants prescribed appropriate treatment at index visit or within 24 hours of index as defined by use of a CDC recommended treatment regimen and/or a treatment approved for that indication by the US FDA for vaginitis/vaginosis. A previous study found that 40% of women received inappropriate treatment for vaginitis in community practice settings (18). We anticipate a higher proportion of women are being treated appropriately at the proposed study site since UPMC MWH is a teaching hospital that specializes

in healthcare for women. For the present study, we are making the assumption that 75% of women will receive appropriate treatment in the standard of care arm. We hypothesize that women in the study arm in which study clinicians and patients are provided with same day access to Xpert® Xpress MVP will have a higher proportion of women receiving appropriate treatment. A sample size of 150 participants in each arm will have 91% power to detect a difference of at least 15 percentage points in each arm of the study based on a Fishers exact test evaluated at the 2-sided .05 significance level.

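### The primary endpoint is scored against a reference that contains the test Arm 2 acts on, and the plan conflicts on how to count participants in whom MVP and BD MAX disagree; both readings lean towards Arm 2

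*Combined protocol and SAP*

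**What the plan says.** Section 2.1 defines appropriate treatment by the diagnosis from the self-collected swabs and states: "A positive result from both FDA cleared molecular tests (Xpert® Xpress MVP; BD MAX™ Vaginal Panel) will be considered the gold standard". Section 4.2 says that BD MAX serves the primary objective and that treatment is judged "based on diagnosis from concordant NAAT (Xpert® Xpress MVP and BD MAX™ Vaginal Panel) results from the self-collected enrollment swabs".

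MVP is also the Arm 2 intervention. Section 5 has Arm 2 providers "asked to use the result of the FDA cleared test for diagnosis and treatment", although they are not obliged to do so. Arm 1 providers receive MVP only after the two-week contact. BD MAX is run in both arms and is never shown to providers or participants.

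Section 7.2, the primary analysis, names Fisher's exact test and has no rule for discordant results. Section 7.3, headed secondary and exploratory analyses, repeats the both-positive standard, sends discordant samples for retest from the reserve sample, and adds: "Samples which are discordant after retesting will be evaluated separately". No analysis against a reference without MVP is planned.

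**The concern.** One arm acts on a component of the standard by which it is judged. Where MVP and BD MAX agree, an Arm 2 provider who follows MVP with a recommended or approved treatment is scored appropriate by construction. Where they disagree, MVP may have led the provider wrong, and this is exactly where the plan is unclear.

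- **Discordant participants set aside** (Section 4.2 with 7.3): possible MVP errors leave the comparison after randomisation. Arm 1 never saw MVP, so it need not lose a matching block of failures.
- **Discordant participants counted as negative** (Section 2.1): nobody leaves, but an MVP-negative, BD MAX-positive woman becomes reference-negative, so an Arm 2 provider who left her untreated is scored as right.

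At stake is whether a significant primary result would show better treatment as judged by a test that did not guide it.

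**Working it through.** **The plan's own figure.** Section 7.1 states "A sample size of 150 participants in each arm will have 91% power" for a 15-point difference, assumes "75% of women will receive appropriate treatment in the standard of care arm", and has the test "evaluated at the 2-sided .05 significance level". Exact enumeration of the Fisher test at 75% v 90% with 150 per arm gives 91.6%, so the stated power reproduces. With both arms at 75%, the same test rejects in 3.7% of trials. That is the baseline below.

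**Discordance before retest.** Inputs: BV 30%, VVC 34%, TV 7% (Section 3.1); positive agreement (PPA) 93.6% to 99.0% and negative agreement (NPA) 92.1% to 99.8% (Section 1). Assumptions: those agreement figures apply to MVP v BD MAX, the three targets are independent, and disagreement on any target makes the participant discordant.

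Per target: prevalence × (1 − PPA) + (1 − prevalence) × (1 − NPA).

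- Low end: BV 0.30 × 0.064 + 0.70 × 0.079 = 7.45%; VVC 7.39%; TV 7.80%. Any target: 1 − 0.9255 × 0.9261 × 0.9221 = 21.0%.
- Midpoint (96.3% / 95.95%): 11.4%.
- High end: 0.44%, 0.47%, 0.26%. Any target: 1.2%.

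**Reading A: discordant counted as negative.** Further assumptions: full adherence to MVP, no discordance resolved on retest, no treatment is appropriate for a reference-negative woman, and the Arm 1 rate is the same under either scoring. Against BD MAX alone, Arm 2 is right only when all targets agree. Against the both-positive standard, it is wrong only when MVP is positive and BD MAX negative, so its rate is the product over targets of 1 − (1 − prevalence)(1 − NPA).

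| Agreement | Arm 2 v BD MAX alone | Arm 2 v both-positive | Inflation |
|---|---|---|---|
| Low end | 79.0% | 83.0% | 3.9 points |
| Midpoint | 88.6% | 91.0% | 2.4 points |
| High end | 98.8% | 99.5% | 0.7 points |

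(Inflation is taken from unrounded rates.)

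**Reading B: persistently discordant set aside.** The documents do not give the share *d* still discordant after retest, so 1%, 5%, 8% and 10% are assumptions. Suppose both arms have 75% success over all participants, judged by BD MAX. Among discordant women, assume 10% success in Arm 2, and 75% or 60% in Arm 1. With *s* the success rate in discordant women, the rate among those kept is (0.75 − *s* × *d*) / (1 − *d*), with 150 × (1 − *d*) per arm, rounded down. At *d* = 10%, Arm 2 shows (0.75 − 0.01) / 0.90 = 82.2%.

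| *d* | n per arm | Arm 2 shown | Arm 1 shown (*s* = 75% / 60%) | Fisher rejects (*s* = 75% / 60%) |
|---|---|---|---|---|
| 1% | 148 | 75.7% | 75.0% / 75.2% | 3.8% / 3.8% |
| 5% | 142 | 78.4% | 75.0% / 75.8% | 8.2% / 6.4% |
| 8% | 138 | 80.7% | 75.0% / 76.3% | 16.6% / 11.2% |
| 10% | 135 | 82.2% | 75.0% / 76.7% | 25.4% / 16.3% |

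The estimate moves as well. If concordant participants show 90% v 75%, with the same success rates in discordant women, the concordant-only analysis reports 15 points. Over everyone, the difference is 11.0 to 11.8 points at *d* = 5%, 8.6 to 9.8 at 8%, and 7.0 to 8.5 at 10%. At 10%, for instance, Arm 2 is 0.90 × 0.90 + 0.10 × 0.10 = 82.0%, against 73.5% to 75.0% in Arm 1.

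**The case against.** The strongest reply is that the plan never says anyone leaves the primary analysis. Section 7.2 excludes nobody. The sentence about separate evaluation stands under secondary analyses, speaks of samples rather than participants, and applies only after a retest. This stands. A reader might infer that discordant women are certainly dropped and that 150 per arm shrinks; the documents do not establish either, and on Section 2.1 alone all 150 remain. What survives is that Section 4.2 ties the primary objective to concordant results, so exclusion is a fair reading, and that the alternative also leans towards Arm 2.

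Second, the size rests on inputs the documents lack. A reader might take the 25% rejection rate as the trial's error rate. It is one corner of an illustration. If discordant women are also hard for Arm 1 (50% success) and Arm 2 providers often depart from MVP (30% success), rejection at *d* = 5%, 8% and 10% is 4.1%, 4.7% and 5.3%. The retest matters too: at midpoint agreement with full adherence, if half the discordances resolve, all towards BD MAX, Arm 2 shows 93.9% rather than 100%; if all resolve that way, it shows 88.6% and the bias is gone. The plan does not ensure that outcome.

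Third, requiring two cleared tests to agree is a defensible guard against single-assay error. Section 1 gives BD MAX 90.5% sensitivity and 85.8% specificity for BV, and both panels are NAATs with shared BV targets. A reader might conclude that BD MAX must be the sole primary reference; these figures make that debatable. They do not argue against a prespecified analysis that uses it.

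**Conclusion.** The concern holds as a defect of the reference standard combined with conflicting rules for discordant results. The direction favours Arm 2 on both readings, given that Arm 2 providers largely follow MVP and that Arm 1 does not do equally badly in discordant women.

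The size is open. Counting discordant participants as negative adds about 0.7 to 3.9 points to Arm 2 under full adherence with nothing resolved on retest. Setting them aside does almost nothing at 1% persistent discordance (3.8% rejection against 3.7%) and raises rejection to between 16% and 25% at 10%, under the stated assumptions. The documents do not support a single figure, nor the statement that exclusion from the primary analysis is planned. They do show that the sole primary comparison lacks one consistent scoring rule and any check against a reference free of MVP.

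**What to change.** 1. Reconcile Sections 2.1, 4.2, 7.2 and 7.3 before outcome data are seen. Keep every randomised participant in the primary analysis, under one stated rule for scoring discordant results, by target. State whether the initial or the retest result enters the reference.
2. Report discordance by arm, before and after retest. MVP is run at once in Arm 2 but after storage of up to 17 days in Arm 1, so the rates may differ.
3. Prespecify an analysis of all participants against BD MAX alone, preferably on its initial result, since only discordant samples are retested. Claim superiority only if the result holds there.
4. Keep the concordant-only result as a labelled sensitivity analysis.

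The cost is wording and some extra tabulation; no new samples are needed, because BD MAX is already run in both arms. The downside is that BD MAX's own errors can shrink the difference in the added analysis. With Arm 1 at 75%, full adherence and 150 per arm, its Fisher power is about 84% at midpoint agreement (88.6% v 75%), close to 100% at the high end, and only about 10% at the low end (79.0% v 75%).
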